2.11.8 Vital signs

Vital signs include height (cm), weight (kg), BMI (kg/m²), temperature (°C), pulse rate (beats per minute [bpm]), mean systolic blood pressure (SBP) (mmHg) and mean diastolic blood pressure (DBP) (mmHg). Mean sitting and mean standing SPB/DBP will be derived from the three assessments taken per visit and will be used for analysis and presentation (as recorded in the Vital signs eCRF).

As per [Section 3.4](#) (Definition of Baseline and post-baseline assessments):

Baseline (derived) is defined as the last available assessment (scheduled or unscheduled) prior to the start of the first infusion of study drug, including pre-dose assessments at Day 1.

End of Treatment (derived) is defined as the last available assessment (scheduled or unscheduled) assigned to treatment (expected per protocol at Week 20 + 56-days).

End of Study (derived) is defined as the last available assessment (scheduled or unscheduled) assigned to the study.

Descriptive statistics (see [Section 3.2](#) [Precision and summary statistics]) will be presented for all patients assigned to the SAF analysis set, at each windowed visit with change from Baseline and % change from Baseline at each windowed post-baseline visit and End of Treatment (derived)/End of Study (derived) as relevant. All summaries will be presented for each treatment group and across active bimagrumab treatment groups combined (“Active Total: Safety” - Includes bimagrumab 700 mg, bimagrumab 210 mg and bimagrumab 70 mg), overall and by region.

The mean change from Baseline in vital sign assessments at each windowed post-baseline visit including End of Treatment (derived)/End of Study (derived) together with the associated 95% confidence interval of the mean will be presented graphically, by treatment group and across all four treatment groups combined, for each vital sign, overall only.

The change from Baseline at each windowed post-baseline visit in derived BMI category (unit kg/m²) will be presented as a shift table for each treatment group and across active bimagrumab treatment groups combined (“Active Total: Safety” - Includes bimagrumab 700 mg, bimagrumab 210 mg and bimagrumab 70 mg), overall and by region [REDACTED] at Baseline.

The percentages (%) will be derived relative to the number of patients in the SAF analysis set with data available at Baseline and at the relevant windowed visit.

In general, all vital signs data will be listed in by-patient data listings by treatment group, country, patient and visit/relative study day. Any clinically notable criteria will also be presented in by-patient data listing.

Abnormal vital signs changes

Abnormal vital signs criteria can be found in [Table 3.6](#) (Clinically notable laboratory values, vital signs, ECG intervals and echocardiography).

Newly occurring clinically notable criteria

Newly occurring clinically notable criteria will be presented in a similar manner as described in [Section 2.11.7](#) (Laboratory data). As before, if assessments cannot be made at Baseline due to missing value(s), post-baseline values meeting the clinically notable criterion will be considered as newly occurring.

The incidence of patients per vital sign (SBP [mm Hg], DBP [mm Hg], pulse rate [bpm] and weight [kg]) with at least one newly occurring clinically notable criteria on treatment (at last infusion of study drug expected per protocol at Week 20 + 56-days) will be presented by treatment group and across active bimagrumab treatment groups combined (“Active Total: Safety” - Includes bimagrumab 700 mg, bimagrumab 210 mg and bimagrumab 70 mg), overall only. The percentage (%) per vital signs test will be calculated as the number (n) of patients with at least one scheduled or unscheduled newly occurring clinically notable criteria result occurring after the start of the first infusion of study drug up to and including the last available assessment assigned to treatment relative to the total number of patients “at risk” (in the SAF analysis set). The incidences in the post-treatment follow-up and overall study will be presented in a similar manner, adjusting accordingly.

All newly occurring clinically notable vital signs data will be listed by treatment group, country, patient, and visit with abnormal values flagged.

2.11.9 ECG

All ECGs must be recorded after 10 minutes rest in the supine position. The Fredericia QT correction formula (QTcF) will be used for clinical decisions. A standard 12-lead ECG may contain more than one assessment of a given ECG parameter for any given assessment timepoint, triplicate ECGs being common. When more than one such assessment is available at a given timepoint for a single ECG parameter, the mean of the measured intervals at that timepoint will be used as the patient's result for that timepoint per ECG interval.

Baseline and post-baseline assessments are defined in [Section 3.4](#).

Descriptive statistics (see [Section 3.2](#) [Precision and summary statistics]) for quantitative and qualitative assessments will be presented for all patients assigned to the SAF analysis set, at each windowed visit with change from Baseline and % change from Baseline at each windowed post-baseline visit and End of Treatment (derived)/End of Study (derived) as relevant. All summaries will be presented for each treatment group and across active bimagrumab treatment groups combined ("Active Total: Safety" - Includes bimagrumab 700 mg, bimagrumab 210 mg and bimagrumab 70 mg), overall only.

The mean change from Baseline in ECG assessment at each windowed visit including End of Treatment (derived)/End of Study (derived) and the associated 95% confidence interval of the mean will be presented graphically, by treatment group and across all four treatment groups combined, overall only.

In general, all ECG data will be listed in by-patient data listings by treatment group, country, patient and visit/relative study day. Any clinically notable criteria or findings will also be presented in by-patient data listings.

Abnormal ECG findings

Abnormal ECG findings can be found in [Table 3.6](#) (Clinically notable laboratory values, vital signs, ECG intervals and echocardiography), such as:

- QTc (Fredericia) \geq 450 msec (for males).
- QTc (Fredericia) \geq 460 msec (for females).
- QTc (Fredericia) \geq 500 msec.
- QTc $>$ 30 msec change from baseline or QTc $>$ 60 msec change from baseline.
- PR $>$ 250 msec.

Newly occurring clinically notable criteria

Newly occurring clinically notable criteria will be presented in a similar manner as described in [Section 2.11.8](#) (Laboratory data). As before, if assessments cannot be made at Baseline due to missing value(s), post-baseline values meeting the clinically notable criterion will be considered as newly occurring.

All newly occurring clinically notable ECG findings will be listed by treatment group, country, patient, and visit with findings flagged.

2.11.10 Echocardiography

The following echocardiography assessments will be recorded:

- Left ventricular end-diastolic volume (mL).
- Left ventricular end-systolic volume (mL).
- Left ventricular ejection fraction (%).
- Interventricular septum thickness (mm).
- Left ventricular end-diastolic diameter (mm).
- Left ventricular end-systolic diameter (mm).
- Left ventricular posterior wall thickness (mm).
- Left ventricular anterior wall thickness (mm).
- Left ventricular mass (g).
- Left ventricular mass index (g/m²).
- Relative wall thickness (ratio).
- Fractional shortening (%).
- Left atrial area (cm²).
- Left atrial volume (mL).
- Right ventricular wall thickness (mm).
- Right ventricular diameter in mid cavity (mm).

Descriptive statistics (see [Section 3.2](#) [Precision and summary statistics]) for quantitative and qualitative echocardiography assessments will be presented for all patients assigned to the SAF analysis set, at each windowed visit with change from Baseline and % change from Baseline at each windowed post-baseline visit and End of Treatment (derived) as relevant. All summaries will be presented for each treatment group and across active bimagrumab treatment groups combined (“Active Total: Safety” - Includes bimagrumab 700 mg, bimagrumab 210 mg and bimagrumab 70 mg), overall only.

The mean change from Baseline in quantitative echocardiography assessment at each windowed post-baseline visit including End of Treatment (derived)/End of Study (derived) and the associated 95% confidence interval of the mean will be presented graphically, by treatment group and across all four treatment groups combined, overall only. Only echocardiography assessments with a clinically notable criterion as defined in [Section 3.8](#) (Clinically notable values), by echocardiography assessment will be presented graphically as described above.

In general, all echocardiography data will be listed in by-patient data listings by treatment group, country, patient and visit/relative study day. Any clinically notable criteria will also be presented in by-patient data listing.

Abnormal echocardiography findings

Abnormal echocardiography criteria can be found in [Table 3.6](#) (Clinically notable laboratory values, vital signs, ECG intervals and echocardiography).

Newly occurring clinically notable criteria

Newly occurring clinically notable criteria will be presented in a similar manner as described in [Section 2.11.8](#) (Laboratory data). As before, if assessments cannot be made at Baseline due to missing value(s), post-baseline values meeting the clinically notable criterion will be considered as newly occurring.

All newly occurring clinically notable echocardiography data will be listed by treatment group, country, patient and visit.

2.11.11 X-ray assessment of surgical procedure

X-ray assessment of surgical procedure is an optional assessment, so the number of assessments may be limited. If the number of X-ray assessments are sufficient, descriptive statistics of the X-ray assessment, by windowed visit, treatment group and across active bimagrumab treatment groups combined (“Active Total: Safety” - Includes bimagrumab 700 mg, bimagrumab 210 mg and bimagrumab 70 mg), will be presented.

The following X-ray findings will be recorded:

- Poor intraoperative fracture reduction.
- Loss of reduction/cut out/cut through.
- Fracture impaction.
- Implant loosening.
- Re-fracture.
- Near-implant fracture.
- Implant/screw failure/breakage.
- Soft tissue calcification.
- Non-union.
- Blade/nail disengagement.
- Avascular head necrosis.
- Cement fracture.

All X-ray assessment data will be listed in by-patient data listings by treatment group, country, patient and visit/relative study day.

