5.5.9 Discontinuation of investigational treatment or premature study discontinuation

Patients may voluntarily discontinue the investigational treatment for any reason at any time.

The investigator should discontinue investigational treatment for a given patient if, on balance, he/she believes that continuation would be detrimental to the patient's well-being.

Investigational treatment *must* be discontinued under the following circumstances:

- Use of prohibited treatment as per [Table 5-1](#).
- Any other protocol deviation that results in a significant risk to the patient's safety
- Breaking of the blind (inadvertently or for emergency reasons)
- Severe hypersensitivity reaction occurs
- Liver event definition met as per [Appendix 2](#)
- Deviations from the prescribed dose regimen for investigational treatment with 2 doses missed at any time
- Death
- Withdrawal of consent
- Sponsor decision to terminate (part of) the study

Investigational treatment *may* be discontinued under the following circumstances:

- Emergence of the adverse events that in the judgment of the investigator, taking into account the patient's overall status, prevent the patient from continuing participation in the study
- Any laboratory abnormalities that in the judgment of the investigator, taking into consideration the patient's overall status, prevents the patient from continuing participation in the study

At the time of protocol amendment #2 implementation, patients who have already received their Week 20 infusion of investigational treatment returned to the site at their next scheduled

visit and performed their End of Treatment visit. They continued as per the study visit schedule Table 6.1.

Patients who discontinue investigational treatment are NOT considered immediately withdrawn from the STUDY or to have withdrawn informed consent to participation (described in section 5.5.10). The patient must return approximately 28 days following the patient's last investigational treatment administration to complete the End of Treatment visit assessments (Table 6-1). If the patient was already off-treatment for a longer period, then the End of Treatment visit can be performed without delay. After completing the End of Treatment assessments, patients will enter a 4-week follow up and return for the End of Study visit. If the patient fails to return for these assessments for unknown reasons, every effort should be made to contact him/her as specified in Section 5.5.11.

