During the post-treatment follow up epoch, safety and efficacy assessments will continue until the EoS visit at week 48. .

[figure not shown]
[figure not shown]
[figure not shown]
[figure not shown]

Table 6-1 Assessment schedule

Study Epoch	Screening	Treatment							Post-treatment follow up		Notes
Visit name/study week	Screening / Day -39 to -1	BL/ Rand Day 1	Week 4	Week 8	Week 12	Week 16	Week 20	End of treatment / Week 24 *	Week 36	End of study / Week 48	
Days post-op or post 1st dose	D3 to 42 post- op	1	28	56	84	112	140	168	252	336	
Informed Consent	X										
Verify Inclusion/ Exclusion	X										
Randomization		X									
Demographics	X										
MMSE	S										Source documents only.
Hip fracture history	X										
Medical history	X										
Physical Examination	S				S			S		S	Source documents only.
Blood sample for serology	X										
Blood sample for hematology and chemistry	X		X	X	X			X		X	
Blood sample for hormones	X				X			X		X	
Urine sample	X		X	X	X			X		X	
Vital Signs	X	X	X	X	X	X	X	X	X	X	
Height	X										
Weight	X	X	X	X	X	X	X	X	X	X	
12-lead ECG (triplicate)	X	X			X			X			
Echocardiography								(X)		(X)	Only for patients enrolled

Study Epoch	Screening	Treatment							Post-treatment follow up		Notes
Visit name/study week	Screening / Day -39 to -1	BL/ Rand Day 1	Week 4	Week 8	Week 12	Week 16	Week 20	End of treatment / Week 24 *	Week 36	End of study / Week 48	
Days post-op or post 1 st dose	D3 to 42 post- op	1	28	56	84	112	140	168	252	336	
											before Amendment #3. W48 is to be performed only if W24 reading indicates clinically meaningful abnormality as per central reader's assessment.
Gait Speed	S										Source document only.
SPPB (incl. gait speed)		X	X	X	X	X	X	X	X	X	
DXA		X			X			X			All centrally read.
X-ray	X							X	(X)	(X)	At screening local X-ray taken during or after surgery is to be used. If bone union is incomplete at W24 per central reading, X-rays need to be performed until this is achieved at W36 and potentially W48 as well.
Drug administration		X	X	X	X	X	X				

Study Epoch	Screening	Treatment							Post-treatment follow up		Notes
Visit name/study week	Screening / Day -39 to -1	BL/ Rand Day 1	Week 4	Week 8	Week 12	Week 16	Week 20	End of treatment / Week 24 *	Week 36	End of study / Week 48	
Days post-op or post 1 st dose	D3 to 42 post- op	1	28	56	84	112	140	168	252	336	
AE/SAE reporting	To be recorded as needed										
Medications and medical procedures	To be recorded as needed										

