6.5.7 X-ray assessment of surgical procedure

A historical X-ray done by local practice during or after surgery (in some cases prior to the initiation of screening) will be used by the investigator for eligibility assessment. The summary of the local assessment will be recorded in the Perioperative eCRF and must confirm adequate surgical execution of internal fixation or arthroplasty for fracture repair. Images do not need to be submitted to the central reader vendor.

During the trial, an X-ray of the operated hip will be taken at Week 24 (EoT) visit - as indicated in [Table 6-1](#) - to assess whether fracture healing has been completed (bone union) and whether there are any potential late complications of the surgery. If bone-union is not achieved at Week 24, patient will be followed up at Week 36 and also potentially at Week 48 (EoS), if bone union is still not achieved at Week 36. Additional unscheduled X-rays may also be required if there is any clinical suspicion of delayed/improper fracture healing. Any findings on X-ray need to be reported as adverse events. Specifically, bone non-union seen at Week 36 (delayed fracture healing) needs to be reported as an SAE.

All scheduled and unscheduled X-rays performed after enrollment will be transferred to a central reader (details provided in *Imaging Manual*). Two independent readers of the assigned

vendor will perform a blinded assessment of the images for bone union and a number of pre-specified orthopedic complications. In case of discordant medical opinions regarding the presence or absence of these complications, a third reader will settle a final decision. The central reader may request sites to provide additional X-rays, if available, to support overall assessment of the specific finding.

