Two preclinical studies in rats undergoing osteotomy of the fibula indicate that repeated administration of high doses of bimagrumab (up to 100 mg/kg) may be associated with slight decreases in immature callus size and bone mineral content in skeletally immature (young) animals 4 weeks after surgery, but not in skeletally matured (old) animals. In addition, there were no differences in the size of the mature callus, the radiographic progression of fracture healing, the morphology and biomechanical competency of the fibula when comparing vehicle and bimagrumab treated animals. It is well known in the literature that animal findings do not necessarily translate into clinical findings ([Geusens P et al Rheumatol 2013](#)).

[figure not shown]
[figure not shown]
However, given the first-time testing of bimagrumab in patients undergoing major surgery after a hip fracture, the study will monitor the region of interest with X-ray taken at Week 24. Two independent radiologists (central readers) will assess these images and to confirm completed fracture healing (i.e. bone union) and exclude a number of postoperative orthopedic complications. If bone-union is not achieved at W24, additional X-rays are to be collected at W36, and if needed at W48. Data will be regularly reviewed by an external DMC that is empowered to alert the clinical study team in case of any unexpected safety finding (i.e. trend for delayed fracture healing or increased rate of orthopedic complications).

[figure not shown]
[figure not shown]
Fracture healing as well as osseointegration of non-cemented implants, are both critically dependent on intact bone formation and bone resorption.

[figure not shown]
Although asymptomatic, in order to properly evaluate the increase in lipase or amylase observed in some bimagrumab treated patient and rule out any potential case of pancreatitis, additional monitoring procedure commonly used for pancreatitis diagnostic are included (i.e. laboratory works, clinical presentation and imaging).

[figure not shown]

7 Safety monitoring

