9.5.2.2 Bone Safety Analysis

The incidence of orthopedic complications (i.e. with focus on bone non-union as per X-ray imaging) will be summarized through frequency counts by treatment group. The treatment contrasts will be presented as odds ratios and/or absolute risk differences with corresponding 2-sided 95% confidence intervals depending on the rarity of the event.

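### SAP 2.11.11 calls the hip X-ray optional although the protocol schedules it for all patients at Week 24, so the promised contrast of X-ray non-union is not assured

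*SAP*

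**What the plan says.** **SAP.** Section 2.11.11 states that "X-ray assessment of surgical procedure is an optional assessment, so the number of assessments may be limited". The next sentence begins "If the number of X-ray assessments are sufficient, descriptive statistics of the X-ray assessment" and promises these statistics by visit and treatment group; the section does not define sufficient. Only the listings are unconditional: "All X-ray assessment data will be listed in by-patient data listings by treatment group, country, patient and visit/relative study day".

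**Protocol, schedule.** Section 6.5.7 says "an X-ray of the operated hip will be taken at Week 24 (EoT) visit" and names no subset of patients. Table 6-1 marks Week 24 with a plain X and Weeks 36 and 48 with a bracketed X, explained by the note "If bone union is incomplete at W24 per central reading, X-rays need to be performed until this is achieved at W36 and potentially W48". Patients who stop treatment early must still return "to complete the End of Treatment visit assessments" (Section 5.5.9).

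**Protocol, purpose and analysis.** Section 6.5.12 notes that this is the first use of bimagrumab after major hip-fracture surgery and says that "the study will monitor the region of interest with X-ray taken at Week 24", with two independent central readers confirming union. Section 9.5.2.2 commits to the analysis: "The incidence of orthopedic complications (i.e. with focus on bone non-union as per X-ray imaging) will be summarized" as frequency counts by arm. Contrasts are to be given as odds ratios and/or absolute risk differences with 95% confidence intervals.

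**The concern.** The SAP rests its conditional summary on a premise that the protocol does not share. Fracture healing is the specific bone-safety question in this population, and X-ray assessment is a named measure of the secondary safety objective (SAP 2.1.2, objective 4). If the Week 24 film is analysed as an optional extra, the planned tables need not show how many patients had a readable film, how many were not united on central reading, or how the arms compare on that reading. A patient with no film would then look the same as a patient with a healed fracture. The departure is also undeclared: SAP 2.14 lists changes from the protocol and none concerns the X-ray.

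**Working it through.** There is no stated figure to reproduce. The check sets the texts side by side, with a little arithmetic on the protocol's planning numbers.

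**1. Is the film optional?** Protocol Table 6-1 and Section 6.5.7 schedule it at Week 24/EoT without condition. The words 'if applicable' in the protocol's safety list (Section 6.5) attach to surgical complications, not to hip fracture healing. The note under SAP Table 3.4 repeats the protocol rule: later films are needed only if union is incomplete at Week 24. So SAP 2.11.11 disagrees with both the protocol and the SAP's own windowing table. Its description could fit only Weeks 36 and 48.

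**2. Would numbers be limited?** Protocol Section 4 plans about 245 randomized patients and about 200 completing Week 24.

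- Share with a Week 24 film, completers only: 200 / 245 = 0.816, about 82%.
- If completion is even across arms (an assumption): 0.816 × 70 ≈ 57 in each of placebo, 210 mg and 700 mg, and 0.816 × 35 ≈ 29 in 70 mg.
- Patients who stop early and attend an EoT visit would add to these.

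**3. Is the protocol's contrast secured elsewhere in the SAP?**

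| SAP place | What it gives | What is missing for X-ray non-union |
|---|---|---|
| 2.11.6 | Orthopedic events handled like cardiac events, by arm | Source is the Orthopedic complications eCRF, not expressly the central reading; cardiac odds ratio requires at least 10% |
| 3.11.8 | Odds ratio, 95% CI and p-value for at least one orthopedic event; no gate stated here | All orthopedic events together, not non-union; silent on the gate in 2.11.6 |
| 3.11.4 | Log-rank for first orthopedic event as identified by the adjudication committee | Protocol 8.5 describes a cardiovascular committee; 6.5.7 gives imaging complications to the central readers |

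The SAP does not say whether the odds-ratio gate applies overall or per arm. On planned numbers, 10% of 245 is 24.5, so 25 patients overall, or 7 of 70 in one arm. Section 2.11.6 itself expects orthopedic events to be rare, so the gate could well suppress the contrast. In protocol 9.5.2.2, rarity governs how the contrast is presented, and the by-arm frequency counts carry no condition.

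**4. Which films count as Week 24?** SAP Table 3.4 assigns any film from Day 1 to last infusion + 56 days to Week 24. A patient who stops after one infusion has an EoT visit about 28 days later, near Day 29. That film would carry the Week 24 label, although it was taken about 168 − 29 = 139 days before the target day. Incomplete union on such a film does not mean the same as incomplete union at Day 168.

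**The case against.** The strongest reply is that one loose sentence has little practical effect. About 200 films would meet any ordinary reading of sufficient, so the condition would in practice bite only on the sparse Week 36 and 48 films. All X-ray data are listed regardless. Protocol 6.5.7 requires any X-ray finding to be reported as an adverse event, and non-union at Week 36 as an SAE, so findings should reach the orthopedic event tables and the adverse event of special interest on fracture healing (SAP 2.11.6). Table shells sit in RAP Module 7, which is not available here, and may include an X-ray table.

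Much of this stands, and it rules out some stronger readings:

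- A reader might infer that the SAP has no treatment contrast for bone safety. It has one in 2.11.6 and 3.11.8; the absence is confined to 2.11.11.
- A reader might infer that the Week 24 summary will be dropped for some 200 patients. The wording permits that, but the expected numbers make it unlikely.
- A reader might infer that the SAP mishandles missing Week 24 films. SAP 3.6 sets a general rule of no imputation, and neither document requires an account of films expected and obtained.
- A reader might infer that risk differences are owed for every complication. Protocol 9.5.2.2 allows odds ratios and/or risk differences.

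The reply does not secure a by-arm table of centrally read non-union with a film-based denominator, nor an ungated contrast. Event tables use patients at risk as denominator, so they cannot separate no finding from no film.

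**Conclusion.** The concern holds in a limited form. SAP 2.11.11 misdescribes the Week 24/EoT X-ray, which the protocol schedules for all patients attending that visit. The contrast of X-ray non-union in protocol 9.5.2.2 is not assured by the SAP as written. It is only partly covered by orthopedic event analyses that have a different source, endpoint and denominator, and possibly a 10% gate.

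The size is the scope of the affected data: Week 24 films in about 200 of 245 patients (82%), on the protocol's own completion estimate. No effect on any estimate or error rate can be calculated, because the documents give no expected non-union rate and no split by fixation type. The efficacy analyses are untouched. The conclusion rests on the documents supplied; an unconditional X-ray table in RAP Module 7 would close part of the gap, but the SAP text would still need correcting.

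**What to change.** In SAP 2.11.11:

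1. State that the Week 24/EoT X-ray is scheduled for all patients and that only Weeks 36 and 48 are conditional on incomplete union. Remove the sufficiency condition for Week 24.
2. Tabulate by arm the number of patients with a readable film and the centrally read non-union and other findings, with patients having a readable film as denominator.
3. For non-union, give the odds ratio and/or risk difference v placebo with 95% CI as in protocol 9.5.2.2, without the 10% gate. The exact method already named in SAP 3.11.8 can be used for the odds ratio.
4. Show non-union by fixation type (internal fixation v arthroplasty), since both are enrolled and the denominator relevant to union may differ.
5. Identify films from early EoT visits, because Table 3.4 places them in the Week 24 window.
6. Report non-union at Week 36 or later, the protocol's delayed fracture healing (Sections 6.5.7 and 7.2.1), as its own outcome and not only as follow-up of Week 24.

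Otherwise, declare and justify the departure in SAP 2.14.

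The cost is a few sentences and one extra table, with no new data. Intervals will be wide if events are rare, and the report should say so.

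### Late hip X-rays and Week 48 echocardiograms are triggered by the Week 24 result, but the SAP summarises them by visit without labelling the selected subset or fixing a denominator

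*SAP*

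**What the plan says.** **Imaging schedule.** Protocol Table 6-1 says of X-ray: "If bone union is incomplete at W24 per central reading, X-rays need to be performed until this is achieved at W36", and potentially at Week 48 too. Protocol 6.5.7 gives the same rule and adds a second route: "Additional unscheduled X-rays may also be required if there is any clinical suspicion of delayed/improper fracture healing". For echocardiography, Table 6-1 limits collection to patients enrolled before Amendment 3 and says "W48 is to be performed only if W24 reading indicates clinically meaningful abnormality", as judged by the central reader. No Week 36 echo is scheduled.

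**Echo analysis.** SAP 2.11.10 tabulates values and changes at each windowed visit and plots "The mean change from Baseline in quantitative echocardiography assessment at each windowed post-baseline visit". The plots are limited to parameters with a notable criterion. In SAP Table 3.6 these are ejection fraction, septal thickness and posterior wall thickness. The visit-window table shared by echo and X-ray (SAP Table 3.4) has Week 36 and Week 48 windows. SAP Appendix 4 says data dropped at Amendment 3 go into listings only, and echocardiography is its only row.

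**X-ray analysis.** SAP 2.11.11 plans, if numbers are sufficient, "descriptive statistics of the X-ray assessment, by windowed visit, treatment group". Non-union is among the findings. The section explains the possible shortage thus: "X-ray assessment of surgical procedure is an optional assessment, so the number of assessments may be limited". It states no denominator and does not say that a patient united at Week 24 counts as united afterwards.

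**The concern.** From Week 36 on, who is scheduled to be imaged depends on the Week 24 result. A by-visit table or plot then sets an unselected Week 24 row beside late rows made up mostly of patients who did badly at Week 24, and nothing in the output says so.

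For echo, selecting on an extreme Week 24 value distorts the later mean even if nothing changed. The plotted line could suggest deterioration off drug that is purely a selection effect.

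For X-ray, fracture healing is a central bone-safety question in this trial. If the percentage at Week 36 is taken among films, it measures how often incomplete union persists, not how often patients in the arm are not united. An arm with more incomplete union at Week 24 need not show a higher percentage at Week 36.

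**Working it through.** The documents give no rate for union and no variability for echo, so there is no planned figure to reproduce. The inputs below are assumptions, chosen to show the mechanism.

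**X-ray.** Let N be the patients per arm with a Week 24 film, p the proportion not united at Week 24, and c the proportion of those still not united at Week 36. Assume that all of the latter group, and only they, are filmed.

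- Percentage of filmed patients = (N × p × c) / (N × p) = c. The Week 24 rate cancels.
- Percentage of the arm = p × c.

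| Assumed inputs (placebo v active) | Not united / filmed at Week 36 | % of filmed | % of arm |
|---|---|---|---|
| N = 60; p = 10% v 30%; c = 50% both | 3/6 v 9/18 | 50 v 50 | 5 v 15 |
| N = 70; p = 10% v 20%; c = 50% both | 3.5/7 v 7/14 | 50 v 50 | 5 v 10 |
| N = 70; p = 10% v 20%; c = 60% v 40% | 4.2/7 v 5.6/14 | 60 v 40 | 6 v 8 |

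Varying p from 5% v 10% up to 15% v 30%, with c from 30% to 70% and equal in both arms, leaves the filmed percentages equal. The whole-arm figures run from 1.5% v 3.0% to 10.5% v 21.0%. In the last row of the table the order of the arms reverses.

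**Which denominator applies?** SAP 2.4.1 sets a default of patients who entered the epoch, unless otherwise specified. SAP 2.11.11 specifies nothing else. But two other by-visit outputs, the laboratory shift tables (SAP 2.11.7) and the BMI category shift table (SAP 2.11.8), use patients with data at that visit. A programmer could defend either choice. Even the default denominator merges patients already united with patients who were not united at Week 24 and had no later film. The second group may not be small: Protocol section 4 expects about 200 patients to complete Week 24 and about 120 to complete Week 48, a loss of 80/200 = 40%.

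**Echo.** Assume ejection fraction has mean 62, between-patient SD 6 and within-patient SD 4, with no drug effect and no time trend. Call Week 24 abnormal if the value is below 45 or has fallen by at least 15% relative to baseline. In 2 million simulated patients:

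- selected for a Week 48 echo: 4.6%;
- mean change at Week 24, all patients: 0.0 points;
- mean change at Week 48, selected patients: about -4.6 points.

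Other SDs gave about -3.3 to -5.2. Reading the 15% fall as absolute points gave about -0.3 to -4.6. These ranges cover only the SDs tried, and a larger between-patient SD can bring the artefact close to zero. It never changed sign in the settings tried.

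**The case against.** The strongest counter-case is on the X-ray side, and most of it stands.

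- **Default denominator.** The SAP's general rule points to patients entering the epoch. In the first row of the table, if about 60 per arm enter follow-up, that gives 5% v 15%.
- **Counts are shown.** Qualitative summaries give n as well as % (SAP 3.2). A reader would see 3 v 9 at Week 36 beside 6/60 v 18/60 at Week 24. Selection also raises the non-union percentage; it does not lower it.
- **Healing is analysed elsewhere.** Non-union at Week 36 must be reported as an SAE (Protocol 6.5.7, 7.2.1). Effect on bone fracture healing is an event of special interest. Orthopedic events are summarised on safety-set or at-risk denominators (SAP 2.11.6). Protocol 9.5.2.2 plans non-union incidence by arm with odds ratios and/or risk differences.
- **The limits are partly acknowledged.** The SAP warns of limited X-ray numbers and repeats the trigger under Table 3.4.

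So a reader might infer that delayed healing will vanish from the report, or that late X-rays are handled as if everyone had one. The documents support neither. Nor are late films confined to patients with incomplete union at Week 24, because unscheduled films are allowed.

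What the counter-case leaves open is narrower. The SAP's caveat concerns numbers, not selection. SAP 2.11.6 handles orthopedic events like cardiac ones, where odds ratios and time-to-event results depend on a 10% event threshold. SAP 3.11.4 relies on adjudicated orthopedic events, whereas the committee in Protocol 8.5 is cardiovascular only.

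On echo, Appendix 4 may mean that no Week 48 mean is ever produced. The highlighting it relies on is lost in the text available, so this cannot be confirmed. If it does, it contradicts 2.11.10 rather than correcting it. The derived End of Study value takes the last available echo, so it is less affected. The simulated size also replaces the central reader's judgement with numeric cut-offs, and few patients per arm would be involved.

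**Conclusion.** The concern holds in a limited form. For echo, following SAP 2.11.10 as written gives a Week 48 mean for a subset selected on abnormal Week 24 values. It is not comparable with Week 24, and the section conflicts with Appendix 4. For X-ray, the fault is an unstated denominator and no rule for patients already united. If filmed patients are used, that one table can mask or reverse a between-arm difference that other planned outputs would still show.

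The sizes (50% v 50% against 5% v 15%; about -4.6 ejection-fraction points) rest wholly on assumed rates, SDs and cut-offs. Severity is low: only descriptive safety outputs are touched.

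**What to change.** 1. **Echo.** Reconcile SAP 2.11.10 with Appendix 4. Remove Week 36 and Week 48 from the mean-change tables and plots. Show any Week 48 echo only beside the same patients' Week 24 values, labelled as follow-up triggered by an abnormal reading.
2. **X-ray.** In SAP 2.11.11, report non-union at Weeks 36 and 48 as cumulative status. Use patients with a Week 24 or later central reading as the denominator, count union confirmed at an earlier visit as united, and show incomplete union with no later film as its own category. Give the number filmed. Present the results by fixation type (internal fixation or arthroplasty), already defined in SAP 2.6, since both are enrolled and neither document says how union is read after arthroplasty.
3. **Consistency.** Reconcile the SAP's description of X-ray as optional with the Week 24 film that the protocol schedules, and state where the non-union contrasts of Protocol 9.5.2.2 will be produced.

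The cost is SAP wording and table shells. No new data or change in patient care is needed. SAP 2.4.2 already has follow-up outputs revisited at the final update analysis.
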